8.5.6 Safety Monitoring for Insulin, Oral Antidiabetic Medication and Glucose

All patients on insulin will monitor their glucose levels with a glucometer as per standard practice guidelines and bring their glucometer or glucometer log printout to every clinic visit. In addition, patients who are not on insulin but use a glucometer should also bring their glucometer and/or glucometer log printout to every clinic visit.

- The Investigator or delegate will review the glucometer reading or printout at every clinic visit to evaluate if fasting pre-breakfast self-monitored plasma glucose values exceed threshold values as per the Safety Monitoring Rules for Hyperglycemia below
All diabetic patients will note any changes in their insulin dose and /or oral antidiabetic therapy, as well as any hypoglycemic episode they may experience.
- The Investigator or delegate will ask patients at every clinic visit if they made changes in their insulin dose or oral antidiabetic therapy, and if they experienced a hypoglycemic episode
 - Patients will be instructed on the monitoring and management of hypoglycemic episodes at each visit
 - Documented symptomatic hypoglycemic episodes should be captured as adverse events in the respective CRF. Documented symptomatic hypoglycemia is defined as typical hypoglycemia symptoms accompanied by measured plasma glucose ≤ 70 mg/dL (≤ 3.9 mmol/L)
 - Any changes in insulin dose or oral antidiabetic therapy should be captured into the Concomitant Medication CRF

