8.5.8 Safety Monitoring for Hyperglycemia in Patients with T2DM

If medically appropriate, patients should remain on a stable regimen of anti-hyperglycemic therapy and have either upward dose titration and/or addition of any other anti-hyperglycemic agent(s) only when specific threshold values (listed below) are met and confirmed on subsequent testing (ideally within 1-week of the initial test). Any change to the anti-hyperglycemic therapy should be discussed with the Sponsor Medical Monitor prior to introduction.

Fasting plasma glucose (FPG) and HbA1c are monitored as per visit schedule in [Appendix A](#) (approximately every 3 months) throughout the study. In addition, patients on insulin should self-monitor their plasma glucose (SMPG) routinely on a glucometer. If a fasting pre-breakfast SMPG value exceeds the specific glycemic limit, the patient should check it again on the following 2 days. If all the fasting pre-breakfast values on 3 consecutive days exceed the specific limit, the patient should contact the Investigator and an unscheduled central laboratory FPG measurement and HbA1c should be performed.

The threshold values are defined as:

- FPG > 270 mg/dL (15.0 mmol/L) or
- HbA1c > 9% (for patients with baseline HbA1c < 8%) and HbA1c increase of more than 1% from Baseline (for patients with baseline HbA1c \geq 8 and < 9%)

In case of confirmed FPG/HbA1c above the threshold value, the Investigator should ensure that no reasonable explanation exists for insufficient glucose control and in particular that:

- Plasma glucose was actually measured in the fasting condition (i.e., after at least 10 hours fast)
- Absence of intercurrent disease which may jeopardize glycemic control. In case of an emergency (e.g., surgery, infection), the Investigator can take appropriate measures for glycemic control
- Compliance to treatment is appropriate
- Compliance to diet and lifestyle is appropriate

If any of the above can reasonably explain the insufficient glycemic control, the Investigator should consider the following:

- Investigation and treatment of intercurrent disease (to be reported in adverse event (AE)/concomitant medication parts of the e-CRF)
- Stress on the absolute need to be compliant to treatment
- Organize a specific interview with a Registered Dietician or other qualified nutrition professional and stress on the absolute need to be compliant to diet and lifestyle recommendations

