8.10.1 Concomitant Therapy

A concomitant therapy is any non-protocol specified drug or substance (including over-the-counter medications, herbal medications and vitamin supplements) administered from the time the patient has signed the informed consent at Screening to the end of the post-treatment follow-up period.

Allowed Concomitant Therapy

Use of the following is allowed only if the patient has been on a stable regimen for at least 4 weeks prior to screening and is planned to remain on a stable regimen through the end of the post-treatment follow-up period:

- Lipid lowering drugs (statins, ezetimibe, 0 inhibitors, niacin, fibrates, fish oil, other products containing omega-3 fatty acids (including OTC preparations)
 - The timing of PCSK9 inhibitor and study drug administration should be kept consistent with respect to lipid assessments. The first dose of ISIS 678354 (i.e., Study Day 1) will be scheduled for one day ahead of the next planned PCSK9 inhibitor injection to establish a regular time span between the two medications. PCSK9 inhibitors should be administered one day after administration of the study drug for the whole duration of the study treatment.
- Anti-platelet therapies
- Testosterone, estrogens, progesterone, growth hormone, or progestins.

Disallowed Concomitant Therapy

Use of the following is disallowed:

- Warfarin and other vitamin K antagonists, direct thrombin inhibitors or Factor Xa inhibitors
- Other experimental agents during the study including investigational drug, biological agent, or device within 1 month of Screening, or 5 half-lives of investigational agent, whichever is longer. This includes marketed agents at experimental dosages
- Treatment with any non-Ionis oligonucleotide (including siRNA) at any time or prior treatment with an Ionis oligonucleotide or siRNA within 9 months of Screening. Patients that have previously received only 1 dose of an Ionis oligonucleotide as part of a clinical study may be included as long as \geq 4 months has elapsed since dosing

- Lipoprotein apheresis

Patients should consult with the Site Investigator or designee prior to initiating any new medication, including non-prescription or herbal compounds or any other non-drug therapy.

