All medications will be coded by World Health Organization Drug Dictionary (WHODD) Version DEC2017. The start and stop dates of medications that are recorded on the Concomitant Medications CRF will be used to determine whether the medications are prior or concomitant to the treatment period. Missing or partial dates will be imputed as outlined in Section 3.7.1. Prior medications include medications that started prior to the first dose of Study Drug from the time the patient has signed the informed consent, regardless whether continued while on treatment or not. A concomitant medication is any drug or substance (including over-the-counter (OTC) medications, herbal medications and vitamin supplements) administered between first administration of study drug and the end of the post-treatment follow-up period. A prior medication with an imputed stop date that is missing or on or after date of first dose of Study Drug will also be considered as a concomitant medication. Medications will be classified based on imputed start and imputed stop dates as follows:

1) Prior Medication

Start Date	End Date
< FDD	≥ Inform Consent Date
	Missing

FDD = Date of First Dose of Study Drug

2) Concomitant Medication

Start Date	End Date
< FDD	\geq FDD
	Missing
\geq FDD	Any non-missing stop date
	Missing

FDD = Date of First Dose of Study Drug

Prior or concomitant medications will be summarized separately for all Safety Set by Anatomical Therapeutic Chemical (ATC) class, Preferred Term, treatment group and overall with counts and percentages, sorting by decreasing frequency of all patients. The concomitant medications in on-treatment and on-study period will be summarized respectively.

Prior or concomitant medications will be displayed in patient listings for all Randomized Patients. A listing of ancillary procedures will also be provided. Note that imputed dates will be used for prior and concomitant medications classification. Originally reported dates will be used for listings.

Treatment Exposure and Compliance

Treatment duration and amount of Study Drug received will be summarized by treatment group and overall in Safety Set. Compliance to Study Drug will be summarized by descriptive statistics by treatment group and overall.

Compliance (%) will be calculated as follows:

$100 \times (\text{total volume of Study Drug}) / (\text{total volume of Study Drug scheduled during the treatment period})$.

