3.3.4 Subgroup Analyses of Primary Endpoint

Subgroup analyses (with log-transformation and imputation method) for the primary endpoint are planned as follow:

- Gender: Male, Female
- Age: <65 and \geq 65 years old
- CV history: established CVD (All patients enrolled in original protocol and protocol amendment 1, and Patients enrolled in protocol amendment 2 per Inclusion Criteria 3a), at risk for CVD (Patients enrolled in protocol amendment 2 per Inclusion Criteria 3b)

- Concomitant drugs used in diabetes: yes, no (ATC code: A10, ATC2 text: Drugs Used in Diabetes)
- Concomitant use of insulin and insulin analogues: yes, no (ATC code: A10A, ATC3 text: Insulins and Analogues)
- Concomitant use of triglyceride lowering drugs (fibrates, omega-3 fatty acids): yes, no to include ATC code: C10AB, ATC4 text: Fibrates, and ATC code: C10AX, ATC4 Text: Other Lipid Modifying Agents, Preferred Term: EICOSAPENTAENOIC ACID ETHYL ESTER, FISH OIL, FISH OIL;OMEGA-3 FATTY ACIDS, FISH OIL;TOCOPHEROL, OMEGA-3 FATTY ACIDS, OMEGA-3-ACID ETHYL ESTER.

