3.7.1 Imputation of Missing/Partial Dates

3.7.1.1 Adverse Events

For AEs, the following imputation rules will be applied to impute start dates under conservative principles:

- If year, month and day are all missing then assign the date of first dose of Study Drug
- If month and day are missing, and year is:
 - the same as the year of the first dose of Study Drug then assign the month-day of first Study Drug
 - earlier than the year of the first dose of Study Drug then assign December 31
 - after the year of the first dose of Study Drug then assign January 1
- If only day is missing, and month-year is:
 - the same as the month-year of the first dose of Study Drug then assign the day of first Study Drug
 - earlier than the month-year of the first dose of Study Drug then assign the last day of the month
 - after the month-year of the first dose of Study Drug then assign the first day of the month

Imputation will be performed for the end date only if the day or month is missing (i.e., year is present) for a resolved AE as follows:

- If month and day are missing, and year is
 - the same as the year of the last dose of Study Drug then assign the month-day of the last dose of Study Drug
 - otherwise, assign December 31
- If only day is missing, then assign the last day of the month

If the imputed start date is later than the imputed end date, then set the imputed start date to the imputed end date.

Analysis period (on-treatment and on-study) will be assigned by comparing the imputed AE start date with the period start/end date.

3.7.1.2 *Prior/Concomitant Medications*

For prior/concomitant medications, the following imputation rules will be applied to impute start dates under conservative principles:

- If year, month and day are all missing, then assign the date of first dose of Study Drug
- If month and day are missing and year is:
 - earlier than the year of the first dose of Study Drug then assign December 31
 - otherwise, assign January 1
- If only day is missing, and month-year is:
 - earlier than the month-year of the first dose of Study Drug then assign the last day of the month
 - otherwise, assign the first day of the month

Imputation will be performed for the end date only if the day or month is missing (i.e., year is present) for a stopped prior/concomitant medication as follows:

- If month and day are missing, then assign December 31
- If only day is missing, then assign the last day of the month

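### Three medication subgroups of the primary endpoint, insulin most plausibly, can be set by drugs started after randomisation or even after the Week 25/27 endpoint

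*Combined protocol and SAP*

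**What the plan says.** SAP 3.3.4 lists six subgroup factors for the primary endpoint. Gender, age and CV history are patient or entry characteristics. The other three are medication factors: diabetes drugs (ATC A10), insulin (A10A), and fibrates or omega-3 fatty acids. The insulin factor reads "Concomitant use of insulin and insulin analogues: yes, no". None of the three has a reference date.

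SAP 3.2.5 defines a concomitant medication as a drug "administered between first administration of study drug and the end of the post-treatment follow-up period". Its classification table accepts a start on or after first dose with any stop date or none. It also accepts an earlier start that had not stopped before first dose. The same section adds: "The concomitant medications in on-treatment and on-study period will be summarized respectively".

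On whether such drugs can be started during the study:

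- Protocol 8.5.8 permits "addition of any other anti-hyperglycemic agent(s) only when specific threshold values (listed below) are met" and also says "In case of an emergency (e.g., surgery, infection), the Investigator can take appropriate measures for glycemic control".
- Protocol 8.5.6 says "Any changes in insulin dose or oral antidiabetic therapy should be captured into the Concomitant Medication CRF".
- Protocol 8.10.1 is stricter for lipid-lowering drugs: "Use of the following is allowed only if the patient has been on a stable regimen for at least 4 weeks prior to screening". The regimen must also be planned to stay stable to the end of follow-up. Antidiabetic drugs are not on that list.

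Under SAP 3.1, the End of Treatment (EoT) analysis uses data up to the last EoT visit, and a final analysis follows once follow-up data are locked.

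**The concern.** Whether the drug lowers triglycerides on top of existing insulin or triglyceride-lowering therapy is a question about patients as they were at randomisation. Under the SAP's definition, long-standing users and patients who started later fall into one yes group. Membership can then depend on what happened after treatment began, and the comparison within the subgroup loses the protection of randomisation.

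Insulin is the case to worry about, for two reasons. A new insulin start turns a no into a yes, whereas a diabetic already on treatment is in the A10 yes group from the outset. In addition, protocol 2.3.3 raises the possibility that the drug improves insulin sensitivity, so the need for insulin could itself depend on treatment.

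A start after Week 25/27 cannot change the endpoint value, yet it can still move the patient to the other subgroup. As a hypothetical example, a short insulin course in month 8 would make a Cohort A patient an insulin user for a Week 25 result.

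**Working it through.** The plan states no figure to reproduce here. The check is a reading of the definitions, followed by day arithmetic.

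**Definitions.** SAP 3.3.4 does not cite 3.2.5, so the link between them is an inference, but 3.2.5 holds the only definition in the SAP. The on-treatment and on-study periods apply to summary tables. Both begin at first dose, so neither is a baseline flag, and 3.3.4 does not say which applies. No reading of the documents gives a baseline flag. If the link to 3.2.5 is rejected, the factor has no definition and needs the same repair.

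**How much of the window lies after the endpoint.** Inputs:

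- Primary time point: Day 169 (Week 25, A/B) or Day 183 (Week 27, C/D), from protocol Appendix A and SAP 3.3.1.
- Week 53 EoT visit: Day 365, from Appendix A.
- Follow-up: 13 weeks = 91 days.
- Check on durations: 4 + 52 + 13 = 69 weeks, matching protocol 3.4.

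Share after endpoint = (window end − endpoint day) / (window end − 1).

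| Patient and window | A/B | C/D |
|---|---|---|
| 52 weeks plus follow-up, end Day 365 + 91 = 456 | (456−169)/455 = 287/455 = 63% | (456−183)/455 = 273/455 = 60% |
| 52 weeks, treatment period only, end Day 365 | 196/364 = 54% | 182/364 = 50% |
| EoT at the endpoint visit, plus follow-up | 91/(169+91−1) = 91/259 = 35% | 91/(183+91−1) = 91/273 = 33% |
| Last patient, at the EoT cut-off | 0% | 0% |

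Because treatment lasts 6 to 12 months depending on enrolment date, the length of the window differs between patients.

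**Group sizes.** Each cohort of 25 is randomised 4:1, giving 25 × 4/5 = 20 active patients per regimen and 4 × 5 = 20 pooled placebo. If 10% to 40% use insulin (an assumption), the yes group is 2 to 8 patients per arm, so one reclassified patient counts.

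**Illustration of new starts.** The documents give no start rate. Assuming 2%, 5% or 10% per year, 1 − exp(−rate × 455/365.25) gives about 2.5, 6.0 or 11.7 new yes patients per 100 non-users over the full window. About 58% to 63% of those starts come after the endpoint.

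**Illustration of bias.** Assume 20% baseline users, a 50% reduction in every patient, and log triglycerides 0.3 higher in patients who start before the endpoint.

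- Starts in 15% of active and 5% of placebo non-users: starters make up 0.12/0.32 = 0.375 of the active yes group and 0.04/0.24 = 0.167 of the placebo yes group. The distortion is 0.3 × (0.375 − 0.167) = 0.0625 on the log scale, so the yes group shows 0.5 × exp(0.0625) − 1 = −46.8%, against −50.0% in the no group.
- Start rates reversed: 0.5 × exp(−0.0625) − 1 = −53.0%, against −50.0%.
- Equal start rates: no distortion.

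With a baseline flag the yes group stays at −50%. The no group moves by 0.3 × 0.10 = 0.03 on the log scale, to −48.5% or −51.5%. That shift is the consequence of later starts within a fixed, randomised group; it is not selection into the group.

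**The case against.** The strongest reply is that new insulin starts will be uncommon. Exclusion 15 removes patients with type 2 diabetes and HbA1c of 9.0% or more, a recent change in antidiabetic drugs, or an anticipated need for change during treatment. Protocol 8.5.8 asks for a stable regimen where medically appropriate, allows additions only after confirmed thresholds and discussion with the Medical Monitor, and directs the investigator to look for other explanations. Its emergency clause does not name insulin. For fibrates and omega-3, the stable-regimen rule and the blinding of lipid results (SAP 2.4) make new starts less likely still. All of this stands, and it limits how often the problem will arise.

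It is also true that the window shares are not error rates, that the EoT cut-off limits how much follow-up use enters, and that the distortion of about 3 percentage points needs a threefold difference in start rates. Dose selection (protocol 10.1.4) does not rest on subgroups, and cells of 2 to 8 patients are descriptive under any flag. Finally, the SAP states no purpose for these factors, so treating them as baseline questions is an interpretation.

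These points reduce the weight of the concern. They do not remove the defect: the rule as written lets later events decide membership, and none of these safeguards bars an unplanned start.

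**Conclusion.** The concern holds. Read with the SAP's own definition, three of the six subgroup factors can be set after randomisation and after the endpoint, and insulin is the realistic case. Up to 63% (A/B) or 60% (C/D) of a patient's flag window lies after the endpoint, falling to 0% for the last patient at the EoT cut-off. The effect on the estimates cannot be computed from the documents and is probably small; it depends on start rates and triglyceride differences that the documents do not give. The primary, sensitivity and secondary analyses are untouched. The conclusion rests on applying the 3.2.5 definition to 3.3.4. The change should be made because it is cheap and gives a subgroup that can be interpreted.

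**What to change.** In SAP 3.3.4, define the three medication factors as use ongoing at first dose: start before first dose, and stop on or after first dose or missing.

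Add a rule for incomplete start dates, because the new definition would otherwise create an error that the present one does not:

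- **Wholly missing start.** SAP 3.7.1.2 imputes the date of first dose. Under the current wording such a patient is still a user; under a start-before-first-dose rule a long-standing user would become a non-user. Count these records as baseline use unless the record shows a start after dosing began.
- **Start known only to the month or year of first dose.** SAP 3.7.1.2 sets these to the first of the month or 1 January, so they will usually count as baseline. Flag them.

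List starts during the study separately, by treatment group.

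The cost is a few sentences in 3.3.4 and one date-handling rule. The dates are already collected and imputed, and no clinical procedure changes. The downside is a small chance of misclassifying patients whose start dates are incomplete.

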3.4 Secondary Efficacy Analyses

All analyses of secondary endpoints will be performed on the FAS as primary and PPS as supportive. Secondary efficacy analyses are based on the data collected at the primary analysis time point.

- Percent change from baseline at the primary analysis time point in fasting apoC-III, TC, LDL-C, HDL-C, non-HDL-C, VLDL-C, apoB, and apoA-I will be compared between each ISIS 678354 group and pooled placebo group using an ANCOVA model with log-transformed baseline as covariate. The ANCOVA model without applying any imputation for missing data will use $\log(Y/X)$ as dependent variable, where Y is the post-baseline lipid value and X is the baseline lipid value.
- Proportion of patients who achieve fasting triglycerides ≤ 150 mg/dL (≤ 1.7 mmol/L) at the primary analysis time point with MCMC imputation will be compared between each ISIS 678354 treatment group and pooled placebo group using a logistic regression model with baseline triglycerides as a covariate.
- Proportion of patients who achieve fasting triglycerides ≤ 100 mg/dL (≤ 1.13 mmol/L) at the primary analysis time point with MCMC imputation will be compared between each ISIS 678354 treatment group and pooled placebo group using a logistic regression model with baseline triglycerides as a covariate.

Summary statistics of the observed value, change and percent change from baseline by analysis visit will be performed for fasting apoC-III, TC, LDL-C, HDL-C, non-HDL-C, VLDL-C, apoB, and apoA-I on FAS.

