Safety assessments will be summarized by nominal visit as collected in CRF. For summary tables by nominal visit, only scheduled visits will be used. For multiple records at the nominal (scheduled) visit, the average will be used for continuous values, or the worst will be used for categorical values.

For summary tables of platelet counts by nominal visit, scheduled visits from central lab data and separately, from local lab data will be used. For multiple records at the nominal (scheduled) visit, the average will be used for continuous values, or the worst will be used for categorical values.

3.2.2 *Patient Population Analyzed*

The following analysis sets will be used for the analysis of data as described within each analysis set.

Screened Patients are defined as the patients who sign an informed consent form.

Randomized Patients are defined as the patients who receive a randomization assignment.

Full Analysis Set (FAS): All patients who are randomized and received at least 1 dose of Study Drug (ISIS 678354 or placebo). The FAS represents the practically-feasible intent-to-treat (ITT) population as delineated in International Conference on Harmonisation (ICH) Guideline E9. This population will be used for the analysis of efficacy.

Per Protocol Set (PPS): Subset of the FAS who received prior to the Primary Analysis Timepoint at least 5 monthly doses of Study Drug for patients randomized in Cohorts A and B, or at least 11 every 2-week doses for patients randomized in Cohort C, or at least 22 weekly doses for patients randomized in Cohort D, and who have no major protocol deviations that could compromise the interpretation of efficacy. Major deviations will be determined prior to unblinding for statistical analysis. This population will be used for supportive inferences concerning efficacy.

Safety Set (SS): All patients who are randomized and received at least 1 dose of Study Drug. This population will be used for all safety analyses.

PK Population: All patients who are randomized and received at least 1 dose of ISIS 678354, and have at least 1 evaluable concentration result post first dose. This population will be used for analysis of PK data.

PK Subgroup: A subset of PK population who will undergo additional PK sampling after dose administration on Day 1 and Week 21 (Cohorts A and B) / Week 25 (Cohorts C and D) to evaluate the plasma PK parameters of ISIS 678354.

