3.3.2 Primary Efficacy Analysis

The primary efficacy analysis for the primary endpoint will be the pairwise comparison of percent change from baseline to the primary analysis time point in fasting triglycerides between ISIS 678354 treated groups and pooled placebo group in the FAS.

The percent change from baseline in triglycerides will be analyzed using an ANCOVA model with treatment group as a fixed factor and log-transformed baseline triglycerides as a covariate. The ANCOVA model will use $\log(Y/X)$ as dependent variable, where Y is the post-baseline value of triglycerides and X is the baseline value of the triglyceride. The model will provide an estimate of the log ratio, which will then be converted back to the original ratio scale. The percent change from baseline will then be estimated based on the estimated ratio. Patients with missing primary endpoint will have their fasting triglyceride value imputed using the multiple imputation method described below.

Missing data for the primary efficacy endpoint will be handled by a multiple imputation model that contains the following variables: log-transformed baseline fasting triglyceride value, log-transformed fasting post-baseline triglyceride values, stratified by treatment ([Schafer 1997](#); [Schafer 1999](#)). Imputation of missing data will be conducted under a working assumption of missing at random (MAR), meaning that the propensity for a data point to be missing is not related to the missing data, but it is related to some of the observed data.

The imputations will be performed for post-baseline visits. The Markov Chain Monte Carlo (MCMC) method will be used under the multivariate normality assumption to impute the missing primary endpoint by treatment group (ISIS 678354 treatment group or pooled placebo treatment group). In order to be compliant with the normality assumption, baseline and post-baseline triglyceride data will be log-transformed prior to the imputation process and will be reverted when creating the imputed dataset. The MCMC method will impute 100 datasets in order to estimate the treatment effect, where the median value across the imputed datasets will be used for patients with missing endpoint.

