3.5 Exploratory Efficacy Analyses

All analyses of exploratory endpoints will be performed on the FAS. Percent change from baseline at the primary analysis time point in fasting Lp(a), remnant cholesterol, and ANGPTL3 as log-transformed ratio of post-baseline to baseline value will be compared between each ISIS 678354 group and pooled placebo group using an ANCOVA model with log-transformed baseline as covariate. Summary statistics including observed value, change and percent change from baseline by analysis visit will also be performed.

Table 5 outlines the analysis methods used in each efficacy analysis.

Table 5 Summary of Analysis Methods in Efficacy Analyses

Endpoint	Analysis Type	Log-Transformed Data	MCMC imputation	Population	Model
Primary Endpoint	Primary Analysis	Yes	Yes, assume MAR	FAS	ANCOVA
	Sensitivity Analysis 1	Yes	Yes, assume MAR	PPS	ANCOVA
	Sensitivity Analysis 2	Yes	Yes, assume MAR	FAS	non-parametric Wilcoxon Rank Sum test
	Sensitivity Analysis 3	Yes	Yes, assume MAR	PPS	non-parametric Wilcoxon Rank Sum test
	Sensitivity Analysis 4	Yes	Yes, Placebo: assume MAR. ISIS 678354: missing before discontinuation, assume MAR; missing after discontinuation assume CIR	FAS	ANCOVA
	Sensitivity Analysis 5	Yes	No	FAS	ANCOVA
	Sensitivity Analysis 6	Yes	No	FAS	MMRM
	Subgroup Analysis	Yes	Yes	FAS	ANCOVA
Secondary Endpoints	Secondary Analysis	Yes	Yes for triglycerides; No for other endpoints	FAS and PPS	ANCOVA
Exploratory Endpoint	Exploratory Analyses	Yes	No	FAS	ANCOVA

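### Eight secondary lipids, and the exploratory ones, are analysed on observed cases while triglycerides from the same lipid panel are multiply imputed, so results labelled FAS can rest on different patients and assumptions

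*Combined protocol and SAP*

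**What the plan says.** SAP 3.4 compares percent change at the primary analysis time point in eight lipids between each active group and pooled placebo. The method is an ANCOVA on the log ratio to baseline: "The ANCOVA model without applying any imputation for missing data". The missing-data column of Table 5 (SAP 3.5) confirms the rule for the secondary endpoints, "Yes for triglycerides; No for other endpoints", and enters No for the exploratory endpoints, which are Lp(a), remnant cholesterol and ANGPTL3.

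Triglycerides are treated differently. SAP 3.3.2 states: "Patients with missing primary endpoint will have their fasting triglyceride value imputed using the multiple imputation method described below". The imputation model contains "log-transformed baseline fasting triglyceride value, log-transformed fasting post-baseline triglyceride values, stratified by treatment", and the working assumption is MAR. The two triglyceride responder endpoints, also in SAP 3.4, are analysed "at the primary analysis time point with MCMC imputation will be compared between each ISIS 678354 treatment group and pooled placebo group".

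The population label is the same throughout: "All analyses of secondary endpoints will be performed on the FAS as primary and PPS as supportive". The SAP's FAS requires randomisation and one dose, and no post-baseline lipid value.

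SAP 2.4 and protocol Appendix B place triglycerides and all eight lipids in one lipid panel. Protocol Appendix A schedules that panel at Weeks 5, 9, 13, 17 and 21 before the endpoint. Protocol 10.6.3.2 sets no missing-data rule for secondary endpoints, and neither document gives a reason for the difference.

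**The concern.** ApoC-III is the drug's target, and its reduction will be read beside the triglyceride reduction. As planned, the two rows can come from different patients under different missing-data assumptions. The triglyceride analysis allows dropout to depend on observed interim values. The observed-case lipid ANCOVA adjusts only for arm and baseline, so its contrast is protected against less. A difference between the two results could then reflect dropout handling as well as pharmacology.

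The supporting analyses are also uneven. For triglycerides, observed-case ANCOVA is Sensitivity Analysis 5, one of six, and Sensitivity Analysis 4 addresses informative discontinuation. For the other eight lipids, observed cases are the only approach to missing data. Their one supportive analysis is the PPS repeat, which does not address missing data.

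**Working it through.** The visible documents give no dropout rate, SD or power figure on this point, so there is no plan figure to reproduce.

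**1. Who counts where.** Take a patient who leaves after Week 17 and has no sample in the endpoint window. SAP Appendix A sets that window at Days 156–183 for Cohorts A and B and Days 156–190 for Cohorts C and D, and does not map follow-up visits to an analysis week.

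| Result | Label | Week 5–17 values used in the comparison | Patient contributes |
|---|---|---|---|
| Triglycerides, percent change | FAS | Yes, through imputation | Yes |
| Triglyceride responder endpoints | FAS | Yes, through imputation | Yes |
| ApoC-III and seven other lipids | FAS | No | No |
| Exploratory lipids | FAS | No | No |

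**2. Patients affected.** Active patients per cohort: 25 × 4/5 = 20. Pooled placebo: 4 × 5 = 20. At an assumed 5%, 10%, 15% or 20% missing, 1, 2, 3 or 4 of 20 per group are in the triglyceride analysis but absent from the lipid comparisons.

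**3. Bias.** A simulation with 400,000 patients per arm compared observed-case ANCOVA with imputation from baseline and one interim value within arm. Assumptions, none from the documents:
- interim-to-final correlation 0.7 and baseline correlation −0.3;
- true effect 1.5 SD, with log-ratio SD 0.35;
- where dropout depends on response, a logistic slope of 1.5 per SD.

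Bias in the contrast, in SD units (negative exaggerates a reduction):

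| Dropout mechanism | Observed cases at 5 / 10 / 20% | Imputed at 5 / 10 / 20% |
|---|---|---|
| Completely random | about 0 | about 0 |
| Depends on baseline only | about 0 | about 0 |
| Interim response, same in both arms | 0 | 0 |
| Poor interim response, active arm only | −0.041 / −0.081 / −0.147 | about 0 |
| Poor unseen final response, active arm only | −0.060 / −0.112 / −0.207 | −0.032 / −0.061 / −0.116 |

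For the fourth row, the ratio multiplier is exp(0.35 × bias) = 0.986, 0.972 and 0.950. The true ratio is exp(−0.35 × 1.5) = 0.592, a 41% reduction, which would read as about 42% to 44%. With 20 per group the standard error is √(2/20) = 0.316 SD, so the bias is 0.041/0.316 = 0.13 to 0.147/0.316 = 0.46 standard errors.

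**4. Second setting.** Assume 20 per arm, log SD 0.45, a true effect of −59.3%, a Week 21 to endpoint correlation of 0.5 to 0.7, active-arm leaving driven by poor Week 21 response (16% to 22% missing) and 8% random loss on placebo. Observed cases give −60.6% to −61.7%. The standard error is 0.45 × √(2/20) = 0.142, so the 95% interval around −59.3% runs from about −69% to −46%. The shift is ln(0.394/0.407) = −0.032 to ln(0.383/0.407) = −0.061, which is 0.23 to 0.43 standard errors.

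**5. Precision when there is no bias.** With a fraction d missing at random, the variance factor is 1/(1−d) for observed cases and about 1 + [d/(1−d)](1−ρ²) when an interim value is used. At d = 0.15 these are 1.176 against 1.132 (ρ = 0.5) or 1.090 (ρ = 0.7). The observed-case standard error is larger by √(1.176/1.132) = 1.02 to √(1.176/1.090) = 1.04, that is 2% to 4%.

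**The case against.** The plan is prespecified and consistent, since SAP 3.4 and Table 5 agree. A simpler rule for secondary endpoints in a phase 2 trial of about 100 patients is a defensible choice. Several further points stand:

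- SAP 2.4 keeps lipid results from investigators, sites and patients until the end-of-treatment lock, which makes leaving for poor lipid response less likely. The protocol's stopping rules concern liver, renal, platelet and bleeding findings.
- Protocol 8.8.1 asks for an early-termination visit, ideally within two weeks of the last dose. SAP Table 2 admits unscheduled records within the window, so a fasting sample from Day 156 onward can supply an endpoint value.
- Sensitivity Analysis 5 gives triglycerides on the same observed-case basis, tables must show the number of patients with data (SAP 3.2.2), and the interim lipid values are summarised by visit.

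A reader might infer that the lipid results will overstate the drug's effect. The documents do not support that. It needs dropout related to response, different between arms and concentrated among poor responders. If good responders left instead, the bias would run the other way. For LDL-C, where protocol 2.3.4 reports only an absence of notable increases, there is no clear favourable direction.

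These points limit the size of the problem. They do not explain why interim values inform one analyte and not the others, and Sensitivity Analysis 5 aligns triglycerides with the more restrictive assumption without recovering any lipid data. SAP 3.3.3 itself plans for discontinuation due to adverse events or lack of efficacy, but for triglycerides only.

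**Conclusion.** The inconsistency is real and worth correcting, at modest priority. Results with the same FAS label can rest on different patients and different missing-data assumptions, without a stated reason.

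Bias in the treatment contrast is conditional. It arises only if dropout depends on post-baseline response and that dependence differs between arms. At an assumed 5% to 20% dropout it is then about 0.04 to 0.15 SD, under half a standard error, and it would be unlikely to change the reading of a large apoC-III effect. Otherwise the loss is a few percent of standard error. Dropout, SD, correlation and effect size are all assumptions here. An analysis under MAR removes the bias when leaving depends on observed interim values. In the simulation it only about halved the bias when leaving depended on the unseen final value.

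**What to change.** Amend SAP 3.4, 3.5 and Table 5 before unblinding so that the main analysis of each continuous lipid endpoint uses that analyte's own interim visits under MAR. Either of two routes serves:

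- **MMRM.** Apply the Appendix B model to each analyte, with the contrast against pooled placebo at the primary time point. Sensitivity Analysis 6 then gives triglycerides on the same basis.
- **Multiple imputation.** Fit the ANCOVA in each of the 100 imputed datasets and combine by Rubin's rules. Do not carry over the sentence in SAP 3.3.2 that uses the median across imputed datasets for missing patients, because that discards the between-imputation variation. Derive calculated measures from imputed components, so that remnant cholesterol still equals TC minus the sum of LDL-C and HDL-C (SAP 1.4.3), and likewise non-HDL-C.

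Keep observed-case ANCOVA as the sensitivity analysis, and report the number of patients contributing to each endpoint.

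The cost is SAP wording and extra programming, with no new data. Imputation within groups of about 20 needs convergence checks: baseline plus six post-baseline visits is seven variables, with 7 × 8/2 = 28 variance and covariance terms. The MMRM code estimates one covariance matrix across groups and is less strained. Neither route protects against dropout that is not at random.
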